13.2 Reporting of Adverse Events

Any AEs that occur after a patient has signed the Informed Consent Form and up to 12 weeks after Day 0, must be reported, whether or not it is considered related to any of the study medications.

After 12 weeks post last administration of study treatment, only new onset AESIs, and study treatment-related AEs and SAEs must be reported when they come to the investigator's attention.

All AEs will be reported in the patient eCRFs. If more than one AE occurs, each event should be recorded separately. AEs and/or laboratory abnormalities shall be reported to the Sponsor

according to the reporting requirements and within the time periods specified in the protocol. All AEs will be followed up until resolved or as clinically required.

Specific information about secondary malignancies such as leukaemia, MDS and aplastic anaemia or any other malignancy, will be collected up to 5 years after study medication administration or relapse of disease, including information about treatment given to the patient due to NHL. See also paragraph on Adverse Events of Special Interest in [Section 13.1.7](#).

Death is not defined as an AE but as an outcome of an AE. It is important that the event leading to the death is reported. If death is the outcome of an AE, it will be reported as such for (i) all AEs regardless of relationship to study treatment up to 12 weeks after the last administration of study treatment and (ii) AESI, and study treatment related AEs and SAEs with onset >12 weeks after the last administration of study treatment.

Progression of disease:

- **Part A:** Progression of disease will be reported as an AE until Week 12. Thereafter progression of disease will be recorded in the eCRF and still used as an efficacy endpoint. It will be the SRC who will decide if a fatal outcome of disease progression should be considered as an expected AE. This will depend on the information received and medical consideration.
- **Part B and C:** Disease progression is not reported as an AE if it is clearly consistent with the suspected progression as determined by the protocol. Hospitalisation due solely to disease progression should NOT be reported as a SAE. Any associated symptoms may be reported as adverse events if there is any uncertainty about the symptom being exclusively due to disease progression, or if it does not fit the expected pattern of progression of the disease.

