3.1 General

Summary statistics for continuous variables will consist of number of non-missing observations (n), mean, standard deviation, minimum, 25th percentile, median, 75th percentile and maximum, unless specified otherwise. The precision (number of decimal places) of these variables is defined in the tables, figures and listings (TFLs) shells document – minimum and maximum will be presented to the same level of precision as the raw data; mean, median, percentiles will be presented to 1 additional decimal place; standard deviation will be presented to 2 additional decimal places.

For categorical variables the number and percentage of participants in each category will be presented, based on the number of non-missing observations apart from disposition of participants, protocol deviations, background and demographic characteristics, prior and concomitant medications/procedures and adverse events where the percentage will be based on the number of participants in the analysis set.

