3.3 Derived Data

- *Definition of study day*

Study day is relative to the date of first administration of Betalutin and lilotomab (study Day 1). Therefore, study day for rituximab will be negative.

Note: in the protocol, Betalutin administration day is referred to as Day 0. However, for statistical analysis and to be in line with CDISC requirement, Betalutin administration day will be defined as Day 1, the day before Day 1 is defined as Day -1 and there is no Day 0.

- *Definition of baseline*

Study baseline is defined as the last non-missing value (including scheduled and unscheduled assessments) prior to rituximab dosing. This will usually be the latest value collected at the screening visit.

Betalutin baseline is defined as the last value measured prior to lilotomab and Betalutin dosing. A visit window from day -2 to day 1 (prior to lilotomab and Betalutin dosing) will be used.

- *Incomplete dates*

For calculation purposes, incomplete dates will generally be completed using worst case. For example, the 15th of the month will be used when day is missing and 1st July when day and month are missing.

Further details are given in the relevant sections as required.

- *Non-numeric values*

In the case where a variable is recorded as “>x”, “≥x”, “<x” or “≤x”, then for analysis purposes a value of x will be taken. Where a range of values is quoted the midpoint of the range will be taken.

- *Month windows*

For the laboratory values and change from baseline outputs, to take account of the potential for out of window assessments being conducted due to the COVID-19 pandemic, the following Month labels will be rederived using the table below.

Table 3: LYMRIT-37-01 study, Part B Month Windows

Month	Days relative to the date of Betalutin administration *
Week 8	Days 53 to 61

Week 12	Days 81 to 89
Month 3	Days 78 to 122
Within the first 3 Months	Days 1 to 122
Within the first 6 Months	Days 1 to 213

* (Date of assessment – date of Betalutin administration) +1 if date of assessment is on or after date of Betalutin administration. Otherwise (Date of assessment – date of Betalutin administration).

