3.4 Data Presentation

The TFLs will present the dose regimens (where relevant) as detailed below:

Table 4: LYMRIT-37-01 study, Part B/C Treatment Group Descriptors

Order	Descriptor for Dose Regime (where relevant) to be presented in TFLs	Meaning of Descriptor
1 [1]	40 / 12.5	40 mg lilotomab plus 12.5 MBq/kg Betalutin
2	40 / 15	40 mg lilotomab plus 15 MBq/kg Betalutin
3	100 / 20	100 mg/m ² lilotomab plus 20 MBq/kg Betalutin
4 [1]	Received Rituximab only	Received Rituximab only
5 [1]	Enrolled no treatment	Enrolled but did not receive any trial treatment
6 [1]	Screen failure	Participants in the screened set who failed screening (i.e. are not eligible to join the study per the eligibility eCRF page).

[1] In table summaries, if there is insufficient space to present all treatment groups on a single page, these dose regimens will be presented on the next page.

The data will be summarised in tabular form by Study Part (i.e. B / C) and dose regimen.

Results from scheduled visits will be tabulated. Unscheduled visits will be included in assessments of maximum post-baseline. All assessments will be listed.

Table 5: Populations to be used for output

Type of data	Listings	Summaries
Disposition	Screened set	Screened set
Demographic characteristics and baseline	SAF	SAF, Efficacy Analysis Set
Efficacy	SAF	Efficacy Analysis set

AE's and lab data	SAF	SAF
-------------------	-----	-----

Listings will be sorted by Study Part (i.e. B / C) and dose regimen, patient number and date/time of assessment.

Graphical presentations of the data will also be provided where appropriate.

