3.5.2 Participant Disposition

A summary of participant disposition will be provided. This summary will present number of participants applicable to each of the following:

- Screened set, including screen-failures with reason.
- SAF.
- Efficacy Analysis Set.
- Gave consent for genomic biomarker analysis of tumour tissue (listing only).
- Gave consent to HLA typing (listing only).
- Gave consent for taking part in PK assessments (listing only).
- Gave consent for taking part in dosimetry assessments (listing only).
- Participants who completed the treatment period. (was in study up to Day 92).
- Participants who discontinued during the study treatment period (up to Day 92) (with summary of reasons for withdrawal from the Completion / Withdrawal eCRF page).
- Participants who discontinued after the study treatment period (from Day 93 onwards) (with summary of reasons for withdrawal from the Completion / Withdrawal eCRF page).

The treatment period is from Day 1 to Day 92 inclusive.

All duration derivations (months) are calculated relative to the date of first Betalutin administration using the following formula:

$$\text{Time to data cut off/death/withdrawal (months)} = ([\text{date of data cut off/death/withdrawal} - \text{date of first Betalutin administration}] + 1) * 12 / 365.25$$

For all summaries except the screened summary, the denominator for the percentages of participants in each category will be the number of participants in the SAF. The denominator for the percentages of participants for the screened summaries will be the number in the screened set.

Descriptive statistics for the duration of follow-up (months) will also be included where:

$$\text{Duration of follow-up (months)} = ([\{\text{latest date participant is known to be alive}\} - \text{date of first Betalutin administration}] + 1) * 12 / 365.25 \text{ rounded to 1 decimal place.}$$

Where latest date known to be alive is obtained using all data available for the participant (i.e. eCRF (including unscheduled), response and survival follow-up data).

Completion and withdrawal data, membership of each of the analysis sets along with reasons for exclusion will be listed.

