3.8.1.1 Treatment-Emergent Adverse Events

The focus of AE summarisation will be on treatment-emergent adverse events (TEAE).

Treatment-emergent adverse events AEs (TEAEs) are defined as those adverse events (AEs) occurring after first administration of rituximab or starting prior to the first administration and worsening during treatment. Adverse events with unknown onset date/time will be considered to be treatment-emergent unless the stop date/time is known to be before first administration of rituximab.

A treatment related TEAE is defined as a TEAE that is possibly or probably or definitively/certainly related to the study treatment (Betalutin, rituximab or lilotomab). If the TEAE has a missing relationship it is assumed to be related to the study treatment for analysis

purposes. This will also be derived separately for Betalutin, rituximab and lilotomab. If the TEAE has a missing relationship it is assumed to be related to all applicable study treatments for analysis purposes.

AEs will be classed as occurring in one of five periods:

- Pre-treatment - any AE that starts after the participant has provided written informed consent and that resolves prior to the first administration of rituximab, or an AE that starts prior to the first administration of rituximab and does not increase in severity after the first administration of rituximab.
- Baseline Period: any AE that starts after the participant has the first administration of rituximab but prior to the first administration of lilotomab or Betalutin (study Day 1).
- Lilotomab/Betalutin Exposure Period: any AE that occurs after the first administration of lilotomab or Betalutin (study Day 1) and upto, and including Day 92, or that is present prior to the first administration of lilotomab or Betalutin and worsens after the first administration of lilotomab or Betalutin.
- Rituximab Exposure Period: relates to the combined Baseline Period and Lilotomab/Betalutin Exposure Period (i.e. all AEs that start after the first administration of rituximab).
- Post Betalutin follow-up period: any AE which starts more than 92 days after the start of Betalutin.

All pre-treatment AEs will be excluded from the tabulations but will be fully listed.

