3.8.1.2 Baseline Period Adverse Events

A table will present the number of events and the number and percentage of participants experiencing TEAEs occurring during the baseline period by SOC and PT.

The table will contain an overall summary and will not be split by actual dose regime. SOC and PT will be presented in descending frequency. If a participant experiences more than one TEAE, the participant will be counted once for each SOC and once for each PT.

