3.8.1.3 Lilotomab/Betalutin Exposure Period Adverse Events

The following tables will present the number of events and the number and percentage of participants experiencing TEAEs by SOC and PT for the following break points with separate summaries being produced for each:

- TEAE onset from Day 1 onwards
- TEAE onset from Day 1 to Day 92 (Month 3)

Each table will contain an overall summary. SOC and PT will be presented in descending frequency of the total number of participants with TEAEs. If a participant experiences more than one TEAE, the participant will be counted once for each SOC and once for each PT.

Table 6: LYMRIT-37-01 study, Part B and C Adverse Event Summary Tables

Summary Table	AE onset from Day 1 onwards	AE onset from Day 1 to Day 92 (Month 3)
TEAEs by SOC and PT	X	X
Serious TEAEs	X	X
Study drug related TEAEs (Betalutin, rituximab or lilotomab)		X
Serious study drug related TEAEs (Betalutin, rituximab or lilotomab)		X
TEAEs by CTCAE grading		X
most frequent TEAEs (reported in at least 5% of participants)		X

Adverse event data will be listed in full and will also include a treatment emergent flag (will distinguish pre-treatment, baseline, post treatment (day 93+), an AESI flag, the time of onset and cessation of event relative to first administration of each of rituximab, Lilotomab and Betalutin and duration of AE. Where CTCAE grade changes over time, the worst/most severe will be reported in summary tables.

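### The SAP's Baseline Period for adverse events has no end for rituximab-only patients, and the same patients sit in the implied denominator of the overall Day 1 adverse event summaries

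*SAP*

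**What the plan says.** SAP 3.8.1.1 assigns each adverse event to a period. The Baseline Period takes "any AE that starts after the participant has the first administration of rituximab but prior to the first administration of lilotomab or Betalutin". Study day is counted from that same lilotomab/Betalutin administration (SAP 3.3). The other limits depend on it too: in SAP 3.5.2, "The treatment period is from Day 1 to Day 92 inclusive", and the post-Betalutin follow-up period in 3.8.1.1 is counted from the start of Betalutin.

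The SAP expects patients who never get that far. Table 4 in SAP 3.4 has a group labelled "Received Rituximab only", and the Safety Analysis Set (SAP 3.2.3) admits anyone given any of the three agents. SAP 3.8.1 puts all Part B and Part C patients in the adverse event tables.

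On layout, SAP 3.8.1.2 says of the Baseline Period table: "The table will contain an overall summary and will not be split by actual dose regime". Of the tables that start at Day 1, SAP 3.8.1.3 says: "Each table will contain an overall summary". On denominators, SAP 3.1 lists among its exceptions "adverse events where the percentage will be based on the number of participants in the analysis set", and Table 5 names the Safety Analysis Set for adverse event summaries.

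On collection, Protocol 13.2 narrows reporting late: "After 12 weeks post last administration of study treatment, only new onset AESIs" and treatment-related events need be reported. Before that point all events are collected, whatever their cause.

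**The concern.** A patient who receives lilotomab or Betalutin leaves the Baseline Period about two weeks after rituximab. A rituximab-only patient has no rule that closes the period, so events from a possibly much longer window enter the same single column. No other planned table covers the lead-in, because every table in SAP Table 6 starts at Day 1. A reader would take its percentages as the toxicity of a two-week rituximab lead-in, when they would be a mixture of unequal windows.

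The Day 1 tables have the opposite problem. A rituximab-only patient cannot have an event from Day 1 onwards, yet would count in an overall denominator taken from the whole safety set. The overall percentages would then be too low, and so would any selection made from them under the 5% rule for most frequent events in Table 6.

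**Working it through.** The documents give no figure to reproduce here, so the check is direct arithmetic on their rules.

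**Inputs**
- Lead-in for patients who go on to lilotomab/Betalutin: 14 days (SAP 3.6.5.2), with ±2 days on the Day 0 visit (SAP 2.1.1), so 12 to 16 days.
- Limit for all-cause events after the last study treatment: 12 weeks = 84 days (Protocol 13.2; the same for serious events in 13.3.1).
- r, the rituximab-only share of the safety set: not stated; assumed 2%, 5% or 10%.
- W, the observation time of a rituximab-only patient: not stated; 28 days assumed for an early leaver, 84 days for full collection.

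**Window ratio.** 84/14 = 6.0; across the visit window, 84/16 = 5.25 to 84/12 = 7.0.

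**Lead-in event counts at a constant rate**, relative to 14 days for everyone: [(1 − r)·14 + r·W]/14 = 1 + r(W/14 − 1). This is 1 + r for W = 28 and 1 + 5r for W = 84.

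**Percentage of patients with an event**, for 14-day incidence p and W = 84 (six 14-day blocks): [(1 − r)p + r(1 − (1 − p)^6)]/p.

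**Overall Day 1 percentage**, relative to patients who have a Day 1: 1 − r.

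| r | Count ratio, W = 28 | Count ratio, W = 84 | Incidence ratio, p = 5%, W = 84 | Incidence ratio, p = 30%, W = 84 | Overall Day 1 ratio |
|---|---|---|---|---|---|
| 2% | 1.02 | 1.10 | 1.086 | 1.039 | 0.98 |
| 5% | 1.05 | 1.25 | 1.215 | 1.097 | 0.95 |
| 10% | 1.10 | 1.50 | 1.430 | 1.194 | 0.90 |

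A true 50% incidence from Day 1 would therefore appear in the overall column as 49.0%, 47.5% or 45.0%.

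**The 5% cut-off.** With an assumed 100 patients given lilotomab or Betalutin, 5% is 5 patients. Adding 1 to 10 rituximab-only patients makes it 5.05 to 5.5, so 6 patients are needed if the cut-off is applied to the overall column.

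**After the fix.** With a 16-day end for rituximab-only patients, the count ratio is 1 + r(16/14 − 1): 1.003, 1.007 or 1.014. The overall Day 1 ratio becomes 1.

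**The case against.** The strongest reply is that the 84-day figure is rarely reached. Protocol 13.2 also sets collection at 12 weeks after Day 0, which these patients do not have. Protocol 8.1 has observations on withdrawn patients reported up to withdrawal, after which only survival, long-term toxicity and further therapy are followed. The scheduled visits after rituximab are timed from Day 0. A constant rate is also doubtful: Protocol 4.4 names infusion-related reactions as the most frequent with rituximab, and these arise early, inside the window that all patients share. This stands. It is why the 28-day row is needed and why the 84-day figures are a ceiling for all-cause events. Treatment-related events and events of special interest can still be reported later and would also fall in the period.

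A reader might infer that the main Betalutin results are diluted. The documents do not support that: Table 4 keeps rituximab-only patients as their own group, so the 40/15, 100/20 and 40/12.5 columns are intact, and the Efficacy Analysis Set requires Betalutin (SAP 3.2.2). A reader might also infer that the pooled table leans towards patients who stopped for progression or illness. Nothing in the documents says why patients stopped after rituximab.

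Two further points stand. The SAP never defines the overall summary in 3.8.1.3, so its denominator is an inference. And the full listing, with period flag and onset relative to each agent, lets a reader recover the facts, although it does not correct the tabulated percentages.

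**Conclusion.** The gap is real and minor. Followed as written, the rules leave the Baseline Period open for a group that the SAP itself names, and they pool that group with patients observed for about 14 days. On the natural reading of SAP 3.1 and Table 5, the same group also enters the overall Day 1 denominator.

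The size depends on a count that the documents do not give. For a 2% to 10% share, lead-in event counts are 2% to 10% too high with 28 days of observation. About 10% to 50% is the most that full 84-day collection at a constant rate would give, and it is less for early infusion reactions. The overall Day 1 percentages are low by 2% to 10% relative, however long these patients are followed.

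Only descriptive safety tables in an abbreviated close-out SAP are affected. No test or decision rule rests on them.

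**What to change.** - **SAP 3.8.1.1:** for patients who receive neither lilotomab nor Betalutin, end the Baseline Period 16 days after rituximab (14 days plus the 2-day window).
- **SAP 3.8.1.2:** tabulate their later treatment-emergent events in a separate column for the Table 4 group "Received Rituximab only". No event then leaves the tables, in keeping with the rule in SAP 3.8.1 that all patients are included.
- **SAP 3.8.1.3:** state that the overall column, and any 5% cut-off taken from it, uses patients who received lilotomab or Betalutin as denominator.

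The cost is one extra column, one derived date and a few sentences. The 16-day end does not equalise the lead-in for a patient whose Betalutin was given later than planned; that patient still leaves the period at the actual administration.

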3.8.1.2 Baseline Period Adverse Events

A table will present the number of events and the number and percentage of participants experiencing TEAEs occurring during the baseline period by SOC and PT.

The table will contain an overall summary and will not be split by actual dose regime. SOC and PT will be presented in descending frequency. If a participant experiences more than one TEAE, the participant will be counted once for each SOC and once for each PT.

3.8.1.3 Lilotomab/Betalutin Exposure Period Adverse Events

The following tables will present the number of events and the number and percentage of participants experiencing TEAEs by SOC and PT for the following break points with separate summaries being produced for each:

- TEAE onset from Day 1 onwards
- TEAE onset from Day 1 to Day 92 (Month 3)

Each table will contain an overall summary. SOC and PT will be presented in descending frequency of the total number of participants with TEAEs. If a participant experiences more than one TEAE, the participant will be counted once for each SOC and once for each PT.

Table 6: LYMRIT-37-01 study, Part B and C Adverse Event Summary Tables

Summary Table	AE onset from Day 1 onwards	AE onset from Day 1 to Day 92 (Month 3)
TEAEs by SOC and PT	X	X
Serious TEAEs	X	X
Study drug related TEAEs (Betalutin, rituximab or lilotomab)		X
Serious study drug related TEAEs (Betalutin, rituximab or lilotomab)		X
TEAEs by CTCAE grading		X
most frequent TEAEs (reported in at least 5% of participants)		X

Adverse event data will be listed in full and will also include a treatment emergent flag (will distinguish pre-treatment, baseline, post treatment (day 93+), an AESI flag, the time of onset and cessation of event relative to first administration of each of rituximab, Lilotomab and Betalutin and duration of AE. Where CTCAE grade changes over time, the worst/most severe will be reported in summary tables.

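### SAP Table 6 selects Betalutin-period adverse events only by onset from Day 1, although SAP 3.8.1.1 also assigns to that period earlier events that worsen after lilotomab/Betalutin

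*SAP*

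**What the plan says.** SAP 3.8.1.1 defines a treatment-emergent event (TEAE) with two limbs: onset after the first rituximab dose, or "starting prior to the first administration and worsening during treatment". It then sorts events into periods. The Baseline Period is set by start date alone, from rituximab up to lilotomab/Betalutin. The Lilotomab/Betalutin Exposure Period covers events after dosing up to Day 92, and also any event that "is present prior to the first administration of lilotomab or Betalutin and worsens after the first administration of lilotomab or Betalutin".

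SAP 3.8.1.3 is headed "Lilotomab/Betalutin Exposure Period Adverse Events". It defines two break points, the first being "TEAE onset from Day 1 onwards" and the second onset from Day 1 to Day 92. Both Table 6 column headings repeat the onset condition. The six rows are SOC/PT, serious, related, serious related, CTCAE grade and most frequent. The section adds: "Where CTCAE grade changes over time, the worst/most severe will be reported in summary tables".

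The only other planned adverse-event table, in SAP 3.8.1.2, covers "TEAEs occurring during the baseline period by SOC and PT". It is pooled over regimens and has no serious, related or graded version.

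**The concern.** The period definition and the table filter differ. The definition has an onset limb and a worsening limb; the filter has only the onset limb. Nothing in 3.8.1.3 brings worsened events back in or gives them a new onset date. The rule on changing CTCAE grade implies that some events are single records whose grade moves while the first onset date stays.

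Such records can arise. Events are collected from informed consent (Protocol 13.2, SAP 3.8.1). Screening may start up to 4 weeks before rituximab and can be extended (Protocol 6.3). Rituximab is given at Day -14, and the protocol lists infections and reduced blood counts among its very common reactions (Protocol 4.4).

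Incidence and severity of adverse events is a secondary endpoint for Parts B and C (SAP 2.3). Table 6 holds the only planned serious, related and graded adverse-event summaries. For the SAE and AESI pages, SAP Table 2 asks for raw datasets only. Because the onset filter selects a subset of what the definition covers, any discrepancy can only lower the tabulated counts.

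**Working it through.** The plan gives no figure to reproduce here, so the check passes example events through the written rules.

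**Inputs.** Day 1 is the Betalutin day and there is no Day 0 (SAP 3.3). Rituximab is on Day -14 (SAP 3.6.5.2). The TEAE and period rules come from SAP 3.8.1.1, the baseline-period table from 3.8.1.2, and the Table 6 filter from 3.8.1.3. Each event is one record that keeps its first onset date.

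| Event | TEAE | Baseline Period | Betalutin period | Baseline-period table | Table 6 |
|---|---|---|---|---|---|
| 1. Onset in screening, worsens Day 20 | yes | no | yes | no | **no** |
| 2. Onset Day -7, worsens Day 40 | yes | yes | yes | yes | **no** |
| 3. Onset Day -7, never worsens | yes | yes | no | yes | no |
| 4. Onset Day 10 | yes | no | yes | no | yes |
| 5. Onset Day 120 | yes | no | no (follow-up) | no | Day 1 onwards only |
| 6. Onset in screening, worsens Day -10 only | yes | no | no | no | no |

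**Reading the rows.**
- Rows 3, 4 and 5 behave as intended.
- Row 1 belongs to the Betalutin period by definition and appears in no adverse-event table.
- Row 2 belongs to the Betalutin period and appears only in the pooled SOC/PT baseline table.
- Row 2 also meets two period definitions, although 3.8.1.1 says each event is classed in one period. No precedence is given.
- Row 6 is a side finding: it is a TEAE that fits no period as written. It does not concern Betalutin exposure.

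**Extent in Table 6.** The marks per row are 2 + 2 + 1 + 1 + 1 + 1 = 8 outputs over six rows. All eight are conditioned on onset from Day 1.

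**Effect of one patient.** If k patients have a given preferred term only through such events, its incidence falls by k/N. The documents do not give the regimen group sizes. As assumed values for 40/15, take 61 (the patients in the July 2022 efficacy review, SAP 1) and 87 (the planned number, Protocol 14.1.2.3):
- 1/61 = 1.6 percentage points
- 1/87 = 1.1 percentage points

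The documents do not give k, and it may be zero. A patient with a second event of the same term starting after Day 1 still counts for that term, though possibly at a lower grade.

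**After the change.** Selecting on the period definition brings rows 1 and 2 into Table 6 and leaves rows 3 to 5 as they are.

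**The case against.** **The heading may govern.** The tables sit under the name of a period whose definition includes worsening, and the onset bullets could be read as only splitting Day 1 to 92 from Day 1 onwards. A careful programmer might do this. But the text and both column headings state an onset rule, and that is what will normally be coded. The two sections need reconciling on either reading.

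**A worsening may be entered as a new event.** Protocol 13.1.1 counts worsening of a pre-existing condition as an adverse event, and 13.2 records baseline symptoms that increase in severity. An event entered that way carries its own onset date and passes the filter. This stands as a limit on how many events are affected. It does not remove the problem: neither document requires a new record when an already recorded event worsens, Protocol 13.3.1 treats progression of an SAE as follow-up to the original report, and the SAP's own grade rule presupposes changing records.

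**Cytopenia is covered elsewhere.** A reader might infer that Grade 3/4 cytopenia after Betalutin will be materially understated, given the 56% Grade 3/4 neutropenia at 40/15 in Protocol Table 4-5. The documents do not support that:
- That figure says nothing about events beginning before Day 1.
- Part B entry requires neutrophils of at least 1.5 and platelets of at least 100 x 10⁹/L within 72 hours of rituximab (Protocol 7.1.2, 9.6.2.1).
- Laboratory changes needing no intervention or further investigation are not reported as adverse events (Protocol 13.1.1, 13.4.5), so a mild pre-dose fall would often have no record.
- SAP 3.9.1 counts patients below neutrophil, platelet and lymphocyte thresholds whatever the adverse-event onset.

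That table does not show seriousness or relatedness, and it does not cover infection, bleeding or other non-laboratory events.

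**Nothing is lost from the listings.** This is true. SAP 3.8.1.3 lists every event with onset and cessation relative to each drug. The flag it describes names no category for worsening after Betalutin.

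**Conclusion.** The SAP contradicts itself. Section 3.8.1.1 puts events that worsen after lilotomab/Betalutin in the Betalutin period, and 3.8.1.3 tabulates that period by onset alone. Taken literally, such events are missing from every serious, related and graded table, and some are missing from every adverse-event table.

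This rests on the onset rule being coded as written and on some worsening events being held as single records. The size is unknown and may be small. The direction is known: counts can only be too low. The per-patient shift of 1.1 to 1.6 points depends on the assumed group sizes and is not an estimate of bias.

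The documents do not support saying that a given number of events will be dropped, or that overall Betalutin toxicity is materially understated. The primary endpoint is unaffected. This is a correction worth making before the tables are run.

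**What to change.** Replace the onset condition in SAP 3.8.1.3 and Table 6 with the 3.8.1.1 period definition:

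- Include a TEAE with onset on or after Day 1, or with earlier onset and a CTCAE grade increase after lilotomab/Betalutin.
- Report the worst grade on or after Day 1.
- For worsened events, use the worsening date to place them in the Day 1 to 92 or the Day 1 onwards column.
- State which period takes precedence when an event meets both the Baseline and the Betalutin definitions. Giving precedence to the Betalutin period would fit the heading of 3.8.1.3.

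The documents do not show whether the eCRF records the date of a grade change. If it does not, report events ongoing at Day 1 whose worst grade exceeds the onset grade as a separate, flagged sensitivity count. Do not merge them into the main tables, because some may have worsened between rituximab and Betalutin.

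The cost is a short SAP amendment and a changed filter in the adverse-event program, plus the sensitivity count if worsening dates are missing. No new data collection is needed. Tabulated incidences will stay the same or rise.
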